#### 9.1.2 Deaths, Serious AEs, and AEs That Led to Discontinuation

Final – 22November2011 CONFIDENTIAL Page 26 of 30

Serious treatment emergent adverse events will be summarized. Data will be categorized and presented in a manner similar to that described above for the general AE summaries by treatment group. By subject listings of deaths and serious non-fatal AEs will be presented.

A summary of the number and percentage of subjects with TEAEs leading to treatment discontinuation will also be presented by treatment group. A by-subject listing of all AEs leading to treatment discontinuation will be produced.

### 9.1.3 Adverse Events of Special Interest

Categories of adverse events of special interest (AESIs) include:

- Cardiovascular events: myocardial infarction, cerebrovascular stroke, acute coronary syndrome, cardiovascular death, new or exacerbated congestive heart failure, and etc.
- Hypoglycemic events
- Renal and urinary disorders: nocturia, pollakiuria, polyuria, dysuria, and etc.
- Genitourinary infection: cystitis, urethritis, pyelonephritis, balanitis, vulvovaginitis and etc.
- Liver related events.
- Cancer events.
- Bone fracture events.

All AESIs will be identified by appropriate MedDRA preferred term. A by-subject listing of each category of AESI will be produced. Additional information collected for hypoglycemic events including ADA severity and intervention will be tabulated and listed.

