9.6.2 Adverse event of special interest

9.6.2.1 Genitourinary infections

Genitourinary infections as defined in Section 6.9.7.1 will be summarized. Event terms, signs, symptoms, infectious agent (bacterial or fungal), and treatment undertaken will be documented in the listing.

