9.6.2.3 Hypoglycemia

Severe hypoglycemia as defined in Section 6.9.7.3 will be presented in a listing and summarized.

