9.6.2.4 Renal and Urinary disorders

Events as defined in Section 6.9.7.1 will be summarized. Event terms, signs, and symptoms will be documented in the listing.

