#### 9.1 Adverse Events

### 9.1.1 All and Treatment Emergent AEs

All AEs will be coded using MedDRA version 14.0. A treatment-emergent adverse event (TEAE) is one with a start date on or after the date of the first administration of study drug. Only TEAEs will be included in summary tables. All AEs will be included in listings.

Partial start dates of AE will be assumed to be the earliest possible date consistent with the partial date. In the case of a missing year, the year will be assumed to be the year part of informed consent date of that subject. In the case of a completely missing start date, the start date will be assumed to be prior to date of the first administration of study drug.

In general, AEs will be presented in descending order from the system organ class (SOC) with the highest total incidence (that is, summed across all treatment groups) for any adverse event within the class to the SOC with the lowest total incidence. Within the SOC level, AEs will be presented in descending order from the MedDRA preferred term (PT) with the highest total incidence to the PT with the lowest total incidence. If the total incidence for any two or more PTs within an SOC is equal, the PTs will be presented in alphabetical order. A PT will not be presented if no adverse events occur within the level. At each SOC and PT level of summarization, a subject will be counted once if he/she reports 1 or more events at that level.

A summary of the number and percentage of subjects with TEAEs by severity (mild, moderate, and severe) will be produced. Subjects who experience the same event several times, with different severity will only be counted once according to the maximum severity experienced at each level of summarization. AEs with missing severity will be considered to be severe for the purposes of summarization.

TEAEs will also be summarized in a table by relationship to study drug (related versus not related to study drug). Events reported as not related or unlikely will be categorized as not related; events reported as possible, probable, definite, unknown will be categorized as related. If a relationship to the study drug is missing or unknown, it will be assumed, for the purpose of analyses, to be treatment-related.

A summary of most common TEAEs, defined as any AE on the preferred term level that has an incidence rate >5% among the subjects in either treatment groups, will be produced by treatment.

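### The protocol promises a summary of genitourinary infections and renal/urinary disorders, but the SAP plans only listings, so no planned table counts affected subjects per arm in either category

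*SAP*

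**What the plan says.** The protocol treats a summary and a listing as two outputs. On genitourinary infections, Protocol 9.6.2.1 states: "Genitourinary infections as defined in Section 6.9.7.1 will be summarized". It then sends event terms, signs, symptoms, infectious agent and treatment to a listing. Protocol 9.6.2.4, on renal and urinary disorders, has the same structure: "Events as defined in Section 6.9.7.1 will be summarized", followed by "Event terms, signs, and symptoms will be documented in the listing".

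SAP 9.1.3 names seven categories of adverse events of special interest (AESI) and plans one output for all of them: "A by-subject listing of each category of AESI will be produced". It adds a table for one category only: "Additional information collected for hypoglycemic events including ADA severity and intervention will be tabulated and listed". The genitourinary category is an open-ended group of terms: "Genitourinary infection: cystitis, urethritis, pyelonephritis, balanitis, vulvovaginitis and etc". The renal and urinary category ends in the same open way.

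SAP 9.1.1 counts a subject once at each system organ class (SOC) and once at each preferred term. Its table of most common events keeps a preferred term only if it "has an incidence rate >5% among the subjects in either treatment groups". SAP section 10, on changes to planned analyses, reads as not applicable.

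**The concern.** The protocol itself marks genitourinary infection as an expected harm. Its introduction reports more urinary tract and genital infections with another drug of the class. Its clinical summary reports such infections in the groups given the study drug in phase 2. Protocol 6.9.7.1 and 6.9.7.2 ask sites to evaluate and document both kinds of event carefully.

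The first thing a safety reader will want is the proportion of subjects in each arm who had at least one such event. If the SAP is followed as written, the study report will contain a listing of the events and term-by-term counts, but not that proportion. Because the term list is open, whoever derives the proportion later must also decide which terms belong. SAP 3.6.1 plans an unblinded analysis at Week 24, with results going to some sponsor staff. A list settled after that point could be challenged as chosen with knowledge of the results.

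**Working it through.** The plan states no figure on this point, so the main check is of the text.

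**Step 1: match each category to its outputs.**
- Genitourinary infection: protocol promises a summary and a listing; SAP and shells give Listing 14.3-8.1 only.
- Renal and urinary disorders: protocol promises a summary and a listing; SAP and shells give Listing 14.3-7.1 only.
- Hypoglycemia: protocol 9.6.2.3 says "Severe hypoglycemia as defined in Section 6.9.7.3 will be presented in a listing and summarized"; the shells give Listings 14.3-5.1 and 14.3-6.1 and Table 14.3-1.8. No gap.
- Cardiovascular events: protocol 9.6.2.2 plans no analysis, and SAP 3.1 sends adjudicated events to a separate plan; the shells give Listing 14.3-4.1.
- Liver, cancer and fracture events: the protocol promises no category summary; the shells give Listings 14.3-9.1 to 14.3-11.1.

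Of seven categories, one has a table and six have listings only. The protocol promises a summary for two of those six.

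**Step 2: can the general tables supply the count?** Tables 14.3-1.2 to 14.3-1.7 are organised by SOC and preferred term, and none has a row for an AESI category. Adding term counts does not work. As an illustration with assumed rates, take 150 subjects in an arm and five terms at 2% each:
- each term: 0.02 × 150 = 3 subjects;
- no subject with two terms: 5 × 3 = 15 subjects, 15/150 = 10%;
- the same subjects with all five terms: 3 subjects, 3/150 = 2%.

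The same five rows fit any category incidence from 2% to 10%. An SOC row counts each subject once, but SAP 9.1.3 identifies these events by preferred term, so an SOC row need not match the category. The documents do not say how the terms fall across SOCs.

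**Step 3: can the most-common table supply it?** The cut is above 5%. With 150 per arm, 0.05 × 150 = 7.5, so a term needs at least 8 subjects. With X binomial (150, p), an even spread over five terms, and the terms treated as independent:
- category 10%, p = 0.10/5 = 0.02: P(X ≥ 8) = 0.011; at least one of five terms, 1 − (1 − 0.011)^5 ≈ 0.05;
- category 15%, p = 0.15/5 = 0.03: P(X ≥ 8) = 0.083; at least one of five, 1 − (1 − 0.083)^5 ≈ 0.35.

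Split events sometimes reach this table, but it works term by term and does not give the category count.

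**Step 4: what the missing table would show.** The half-width of the 95% CI for a risk difference is 1.96 × √[p1(1 − p1)/150 + p2(1 − p2)/150]. The rates are assumed, because the documents give none:
- 6% against 2%: difference 4 points, half-width 4.4;
- 10% against 3%: difference 7 points, half-width 5.5;
- 15% against 5%: difference 10 points, half-width 6.7.

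**The case against.** **The word summarised is loose.** It does not say pooled, by arm, or once per subject, and Table 14.3-1.2 does summarise these events by arm at term level. This stands in part: neither document promises the exact table proposed here. But Protocol 9.6.1 already provides tabulations of treatment-emergent events. A separate sentence about summarising each special category adds little unless it means the category.

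**The protocol supplied may not be the one the SAP serves.** It is dated 02 February 2011; the SAP is dated 22 November 2011. The SAP cites Amendment 1 of 11 April 2011 in its schedule of events, and versions of 18 August and 12 September 2011 in shell Table 14.1-1.3. Whether the summary sentences survived cannot be checked here. This stands as a condition on the conflict between the documents. The missing count is a gap in the SAP either way.

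**The information is not lost.** Listing 14.3-8.1 follows the layout of Listing 14.3-1.1: by treatment, with subject identifier and treatment-emergent flag. Subjects can be counted from it over the safety-set total. This stands, and it is why the point is about reporting rather than lost data.

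Four stronger readings are tempting, and the documents do not support them:
- A reader might infer that all AESI categories lack a promised summary. Step 1 shows that this is true of two.
- A reader might infer that split events never reach the most-common table. Step 3 gives about a 35% chance that one term passes at a 15% category incidence, and an uneven split would raise it.
- A reader might infer that the trial leaves its safety question unanswered. The objective is general safety, and tables by severity, relationship, seriousness and discontinuation are planned.
- A reader might want to express the loss as statistical power. The SAP plans no between-arm test of adverse events and the documents give no incidences, so such figures would measure nothing in this plan.

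**Conclusion.** The point holds for genitourinary infections and for renal and urinary disorders. The supplied protocol commits to a summary beside the listing, the SAP and shells keep only the listing, and no change is declared. No planned table gives the number and percent of subjects per arm with at least one event in either category.

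The size is modest. Two of seven categories are affected, the efficacy conclusions are untouched, and the count could be made by hand once someone decides which terms belong. It is still worth correcting, because the protocol flags genitourinary infection as a harm to watch.

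The finding of a conflict assumes that the summary commitment remains in the later protocol versions. For the renal category it also assumes that Protocol 9.6.2.4 means the events under its own heading, since its cross-reference points to the genitourinary section, 6.9.7.1, and not to 6.9.7.2. The incidences in the working are assumptions used only for illustration.

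**What to change.** - Add one descriptive table to SAP 9.1.3 and the shells, on the safety analysis set. For each arm, give the number and percent of subjects with at least one treatment-emergent event, with the risk difference and 95% CI. Include genitourinary infection, with urinary and genital infections as separate rows, and renal and urinary disorders.
- Replace the open-ended category definitions with preferred-term lists, fixed and dated before the Week 24 unblinding.
- Check the summary commitment in the later protocol versions that the SAP cites. If it was withdrawn, record that; the table is still worth adding.
- Correct the cross-reference in Protocol 9.6.2.4 from 6.9.7.1 to 6.9.7.2. Protocol 9.6.2.3 has the same kind of slip: it cites 6.9.7.3, the cardiovascular section, for hypoglycemia, which is defined in 6.9.7.4.

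The cost is one extra table and the work of agreeing the term lists. The events are already coded, and no new data are needed.

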#### **9.2** Labs

### 9.2.1 Hematology, Chemistry and Urinalysis

Laboratory parameters include the following tests: hematology, chemistry, and urinalysis. Established or generally acknowledged methods, normal ranges, and quality control procedures will be supplied by the local and central laboratory for the study records.

Hematology parameters used in summaries include hematocrit, hemoglobin, platelet count, red blood cell (RBC) count, and white blood cell (WBC) count with differential. Chemistry

Final – 22November2011 CONFIDENTIAL Page 27 of 30

parameters (including lipids) used in summaries include albumin, ALT, AST, blood urea nitrogen, calcium, bicarbonate, chloride, direct bilirubin, glucose, magnesium, phosphorus, potassium, sodium, total bilirubin, total protein, uric acid, total cholesterol, LDL cholesterol, HDL cholesterol, triglycerides, and ApoB. Urinalysis parameters used in summaries include appearance, bilirubin, color, glucose, ketones, microscopic examination of sediment, nitrites, occult blood, pH, protein, specific gravity, and urobilinogen.

All laboratory parameters will be summarized for each treatment group, at every assessed time point using descriptive statistics and graphical displays of the means and standard deviations over time. In addition, for hematology and chemistry laboratory parameters, changes from baseline in these quantitative tests will be summarized by treatment group and at every assessed post-baseline time point.

Shift tables will be developed by first classifying the subject laboratory results as low, normal, or high in comparison to the applicable laboratory reference range. The number and percentage of subjects with indicated shifts (low, normal, high) in their results from baseline to each post-baseline assessment will be presented for all hematology, chemistry and applicable urinalysis parameters. All laboratory data will be listed.

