Hypoglycemia will be defined as any FPG or SMBG value < 70 mg/dL.

Any increase in liver function tests (AST, ALT, or bilirubin) greater than 3X the ULN for the laboratory utilized will be considered a clinical laboratory adverse event.

Increase in creatinine from baseline by 0.5 mg/dL or more will be reported as a laboratory adverse event.

Severity: Adverse events will be graded on a 3-point scale and reported as indicated on the CRF. The intensity of an adverse experience is defined as follows:

- 1 = Mild: Discomfort noticed, but no disruption to daily activity.
- 2 = Moderate: Discomfort sufficient to reduce or affect normal daily activity.
- 3 = Severe: Inability to work or perform normal daily activity.

Study Drug Causality: Relationship of an adverse event to treatment will be assessed as follows:

- Definite: There is a reasonable causal relationship between the study drug and the AE, when the event responds to withdrawal of the study drug (dechallenge), and recurs with rechallenge by administration of the study drug.
- Probable: There is a reasonable causal relationship between the study drug and the AE. The event responds to dechallenge. Rechallenge not required.
- Possible: There is a reasonable causal relationship between the study drug and the AE. Dechallenge is lacking or unclear.

Confidential Page 30 of 61

- Not Likely: There is a temporal relationship to study drug administration, but there is not a reasonable causal relationship between the study drug and the event.
- Unrelated: There is not a temporal or causal relationship to the study drug administration.

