**Table 1: Schedule of Events** 

		ening un-in		Treati	nent w	eeks 1	to 24			Treati	nent w	eeks 25	to 96		Follow Up 
Visit Number	1	2	3	4	5	6	7	8	9	10	11	12	13	14	15
Time to Randomization Visit (weeks) 	-5	-2	0	2	6	12	18	24	36	48	60	72	84	96	1 wk f/u
Informed Consent	X														
Screening for I/E criteria	X	X	X												
Medical History	X														
Diet & exercise counseling 		X				X		X		X		X			
Diary & glucometer record review			X	X	X	X	X	X	X	X	X	X	X	X	X
Discontinue anti-diabetic medication		X													
Randomization			X												
Physical exam 	X					X		X		X		X		X	X
Vital signs	X	X	X	X	X	X	X	X	X	X	X	X	X	X	X
ECG	X		X					X			X			X	X
Dispense study medication		X	X		X	X	X	X	X	X	X	X	X		
Blood draw for clinical lab test 	X		X	X	X	X	X	X	X	X	X	X	X	X	X
Urinalysis 	X		X	X	X	X	X	X	X	X	X	X	X	X	X
NMP22 testing 	X		X					X		X		X		X	
$AE^7$			X	X	X	X	X	X	X	X	X	X	X	X	X
Con Med		_	X	X	X	X	X	X	X	X	X	X	X	X	X

Screening period may last up to 21 days (V1 to V2), Run-in period is to be 14±3 days (V2 to V3), V3 to V8 window is ±3 days, all other visit windows are the nominal duration from randomization ± 6 days.

Glucose meter will be dispensed at visit 2. Training on using glucometer and recording hyper- or hypoglycemia will be conducted on visit 2.

- A complete physical examination will be performed by the investigator at screening and at the termination visit. An abbreviated physical examination will include body weight and general assessment of the skin, heart, lungs and abdomen. Abbreviated physical examinations will be performed by the investigator at all other time points, unless clinically indicated.
-  Blood sample for these lab tests at the designated visit are listed as following. Fasting state must be confirmed.
  - V1: CBC, electrolytes, BUN, creatinine, Lipids (TG, TC, HDL-C), ALT, AST, bilirubin (total and direct), PT, HbA1c, FPG, TSH, Hepatitis Screen (HBsAg, HBcAb, HCV), serum pregnancy for women of childbearing potential
  - V3: CBC, electrolytes, BUN, creatinine, Lipids (TG, TC, HDL-c), ALT, AST, bilirubin (total and direct), HbA1c, FPG
  - V4: CBC, electrolytes, BUN, creatinine, HbA1c, FPG
  - V5: CBC, electrolytes, BUN, creatinine, HbA1c, FPG
  - V6: CBC, electrolytes, BUN, creatinine, Lipids (TG, TC, HDL-c), ALT, AST, bilirubin (total and direct), HbA1c, FPG
  - V7: CBC, electrolytes, BUN, creatinine, HbA1c, FPG

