  - V8-V15 and ET: CBC, electrolytes, BUN, creatinine, Lipids (TG, TC, HDL-c), ALT, AST, bilirubin (total and direct), HbA1c, FPG. PT only at V8, and V15 or ET.
-  Clean catch sample to be collected at each visit and sent to the central lab. Urine drug screen on screening (visit 1). On-site urine dipstick to be performed at all visits except V2.
- NMP22 testing will be performed at screening (V1), randomization (V3), and at weeks 24 (V8), 48 (V10), 72 (V12), and 96 (V14) or when clinically indicated. For subjects who do not have baseline NMP22 testing following Protocol Amendment 1 (11 April, 2011), NMP22 testing will be performed in the next visit or within 4 weeks after Amendment is approved, whichever comes first.
- Adverse events of special interest are specified to be:
  - Cardio- and cerebro- vascular events,
  - Genitourinary infections
  - Increase in creatinine from baseline by 0.5 mg/dL or more
  - Increase in ALT, AST or bilirubin to >3x ULN
- Visit to be conducted one week after last dose of study drug whether subject early terminates from study or completes V14.

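### The SAP does not name creatinine in its chemistry summaries, and it plans no by-arm count, derived from laboratory values, of its two laboratory-defined adverse events of special interest

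*SAP*

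**What the plan says.** SAP 9.2.1 introduces its chemistry list as the parameters included in summaries. It begins "albumin, ALT, AST, blood urea nitrogen, calcium, bicarbonate, chloride, direct bilirubin, glucose, magnesium, phosphorus, potassium, sodium, total bilirubin" and ends "total protein, uric acid, total cholesterol, LDL cholesterol, HDL cholesterol, triglycerides, and ApoB". Creatinine appears in neither part. The section then says that all laboratory parameters will be summarized by treatment group at each time point, that hematology and chemistry changes will be summarized, that shift tables will classify results as low, normal or high, and that all laboratory data will be listed.

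Creatinine is collected throughout. The footnotes to SAP Table 1 name it at screening, at baseline and at every later laboratory visit, for example "V4: CBC, electrolytes, BUN, creatinine, HbA1c, FPG".

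The AESI footnote to SAP Table 1 has four entries, two of them laboratory thresholds: "Increase in creatinine from baseline by 0.5 mg/dL or more" and "Increase in ALT, AST or bilirubin to >3x ULN". SAP 9.1.3 gives a different set of categories. Its renal category names urinary symptoms and is left open-ended, and its liver category refers only to liver-related events. It states: "All AESIs will be identified by appropriate MedDRA preferred term". The planned output is: "A by-subject listing of each category of AESI will be produced". Only hypoglycemia is also tabulated.

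Protocol 6.9.1 makes both thresholds reportable. For creatinine: "Increase in creatinine from baseline by 0.5 mg/dL or more will be reported as a laboratory adverse event". It likewise treats liver tests above 3 times the upper limit as laboratory adverse events.

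**The concern.** A threshold on a measured value is best counted from the measured values. If it is found through preferred terms, the count depends on a site noticing the crossing, reporting it, and having it coded to a term that the AESI search picks up. A silent laboratory change will not emerge from the open question about how the subject has felt (Protocol 6.9.2). It relies on the investigator's review of laboratory results.

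At stake is the renal and hepatic safety comparison in a 96-week placebo-controlled trial of a drug that inhibits a renal transporter. The plan itself singled out these two thresholds and excludes subjects with eGFR below 50. If the cut-offs are never applied to the data, the by-arm answer depends on how completely sites reported. If creatinine is also left out of the summaries, its by-arm changes and shifts would be missing too.

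**Working it through.** The plan states no figure for this point, so the check compares lists and outputs.

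1. **Chemistry lists.** Protocol Table 1 (section 6.7.1) has 24 serum chemistry entries. SAP 9.2.1 has 14 in the first part of its list and 7 in the second: 14 + 7 = 21. The difference is 24 − 21 = 3: creatinine, fasting plasma glucose and HbA1c. The last two are analysed as efficacy endpoints in SAP section 7. Creatinine is therefore the only safety chemistry analyte not named. Nothing in the SAP list is absent from the protocol list.

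2. **Data available.** By the SAP Table 1 footnotes, creatinine is drawn at visits 4 to 15, which is 12 scheduled post-baseline visits. ALT, AST and bilirubin are drawn at visit 6 and visits 8 to 15, which is 1 + 8 = 9.

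3. **AESI lists.** Two of the four AESIs in the SAP Table 1 footnote are laboratory thresholds. SAP 9.1.3 states neither cut-off.

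4. **Planned outputs against the two thresholds.**

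| Planned output | Compared by arm | Source | Applies the cut-off |
|---|---|---|---|
| Chemistry values and changes (Table 14.3-2.2) | Yes | Laboratory values; creatinine uncertain | No |
| Chemistry shifts (Table 14.3-2.5) | Yes | Laboratory values; creatinine uncertain | No: low/normal/high |
| Treatment-emergent adverse events by preferred term (Table 14.3-1.2) | Yes | Site reports | Not separately |
| Renal and liver AESI listings (14.3-7.1, 14.3-9.1) | No counts | Site reports | No |
| Chemistry listings (14.3-12.2, 16.2-9.2) | No counts | Laboratory values | No |

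Tables giving a by-arm count of either threshold from laboratory values: 0.

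5. **Can the shift table stand in?** No. Where the reference interval is wider than 0.5 mg/dL, creatinine can rise by that amount and stay normal. A subject already above range stays high whatever the rise. For the liver tests, exclusion criterion 7 removes only values at or above 3 times the upper limit. A subject can therefore enter above normal, cross the threshold, and still appear as high to high.

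6. **Can the preferred-term table stand in?** Only in part. It misses unreported crossings. It can also mix in lesser changes, because Protocol 6.9.1 makes any laboratory change that the investigator judges abnormal for that subject an adverse event.

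**The case against.** A reader might infer that these events would not be counted by arm at all. The documents do not support that. Protocol 6.9.1 makes both thresholds reportable, and SAP 9.1.1 counts treatment-emergent events by preferred term, with a column per arm in the shell. Reported cases therefore reach a by-arm table. The liver tests are also named in 9.2.1 and have by-arm change and shift outputs.

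A reader might also take the 9.2.1 list as closed, so that creatinine is certainly excluded. The list is introduced as what the summaries include, and broader sentences follow it. The chemistry shells name no analytes, whereas the vital-signs shell explicitly limits its parameters to three. Leaving out creatinine may be an oversight that programming would correct. What stands is ambiguity. Protocol 9.6.3 points to section 6.7 for the complete laboratory list, and SAP section 10 records no change.

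Nor does the SAP clearly delete the creatinine AESI. It stays in the Table 1 footnote, and the 9.1.3 categories are open-ended. The two lists are misaligned.

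Finally, the renal microvacuolization in monkeys is weak support for creatinine as the marker. Protocol 1.1.1 says that it occurred without clinical chemistry correlates and that the renal effects generally reversed. The case rests on the plan's own choice of thresholds.

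These objections narrow the point. None of them supplies a threshold count from laboratory values.

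**Conclusion.** The point holds in limited form. Creatinine is the one safety chemistry analyte not named in SAP 9.2.1, and whether it will be summarized is unclear. Two of the four AESIs in the SAP schedule are laboratory thresholds, and neither has a planned by-arm count from laboratory values. Followed as written, the preferred-term rule misses crossings that sites do not report and may mix in lesser changes.

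The number missed cannot be estimated, because the documents give neither event rates nor reporting completeness. If every crossing were reported and coded to a recognizable term, nothing would be lost except separation from sub-threshold events.

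The protocol supplied is dated 02 February 2011, while the SAP cites later protocol versions that were not supplied. I assume that the reporting rule in Protocol 6.9.1 and the chemistry list were unchanged. The mismatch between SAP Table 1, 9.1.3 and 9.2.1 does not depend on that assumption. The primary efficacy analysis is unaffected.

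**What to change.** - In SAP 9.2.1, name creatinine in the chemistry list.
- Align the AESI footnote to SAP Table 1 with SAP 9.1.3, so that both carry the same categories and both laboratory cut-offs.
- In 9.1.3, state that laboratory-defined AESIs are identified from laboratory values in addition to reported preferred terms.
- Add one table on the safety analysis set: number and percent of subjects per arm with any post-baseline creatinine rise of 0.5 mg/dL or more, and with any post-baseline ALT, AST or bilirubin above 3 times the upper limit of normal. Use the shells' baseline definition. State that repeat and unscheduled records count, because SAP 5.4.3 otherwise keeps one record per analysis visit.

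The cost is SAP wording and one extra table; the data are already collected. Summaries of eGFR would be optional and are not needed to close this gap.
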